13.1.5. Statistical Analyses / Methods

Details of the planned displays are provided in Appendix 12 and will be based on GSK Data Standards and statistical principles.

The endpoints / variables defined in Section 13.1.1 will be summarised using descriptive statistics, graphically presented (where appropriate) and listed.

Longitudinal model

The ratio to baseline for the following systemic biomarkers will be analysed using a Bayesian MMRM analysis using the log transformed data including only the placebo and GSK2330811 300mg arms:

- Pro-C3
- Pro-C6
- PINP
- ELF
- COMP
- PIIINP
- IL-6
- MCP-1 (Rename MCP-1 as CCL2 for displays)
- CCL-18

Non-informative priors will be used in these analyses, specifically the prior for the regression coefficient will be normally distributed with mean 0 and a variance of 10^6 . The variance-covariance matrix for the within subject error across the visits will use an inverse-Wishart prior distribution, consisting of the identity matrix and the degrees of freedom will be the number of visits included in the model.

The models will be adjusted for the following covariates: MMF use at day 1, baseline value, treatment, visit, treatment by visit and baseline by visit interactions.

201247

The change from baseline within each treatment group and the difference in the change from baseline across the treatment groups (GSK2330811 300mg – placebo) will be calculated and are back transformed to give the ratio to baseline and the ratio of the change relative to placebo respectively.

Posterior medians and equal tailed 95% credible intervals will be presented. In addition, the probability the ratios are <1 and fold changes (Posterior Medians, as ratio < 1 then fold change is -1/ratio otherwise fold change is ratio) will also be calculated. The line plot of the adjusted posterior medians \pm credible intervals at each visit will be presented.

ANCOVA

The ratio to baseline of log transformed and change from baseline of linear data for the following skin histology and gene expression mRNA sequencing endpoints will be analysed using a Bayesian ANCOVA analysis including only the placebo and GSK2330811 300mg arms:

- Alpha SMA (Excluding Insufficient samples)
- COMP
- CCL2
- 2GSSc
- Disease Signatures GSVA Scores (Upregulated and Downregulated)
- Lung Fibrosis Signature GSVA Score
- Cell Modular Signatures GSVA Scores (Fibrosis, M1-Macrophage and M2-Macrophage)

Non-informative priors will be used in these analyses, specifically the prior for the regression coefficient will be normally distributed with mean 0 and a variance of 10^6 . The prior for the variance parameter will be an inverse-gamma (shape=0.001, scale=0.001).

The models will be adjusted for the following covariates: MMF use at day 1, baseline value and treatment.

Nature of Data	Output Presentation
Log Transformation	 The change from baseline and difference in the treatment groups (GSK2330811 300mg – placebo) will be back transformed to give ratio to baseline and ratio of the change relative to placebo respectively. Posterior medians, equal tailed 95% credible intervals, probability that ratios < 1 and fold change (i.e., Posterior Medians, as ratio < 1 then fold change is -1/ratio otherwise fold change is ratio) will be presented.
Linear	 Change from baseline and the difference in the treatment groups (GSK2330811 300mg – placebo) will be calculated. Posterior medians and equal tailed 95% credible intervals will be presented. Except for Downregulated GSVA score, the probability that difference < 0 will be calculated. For Downregulated GSVA score, the probability > 0 will be calculated.
201247

The plot of the adjusted posterior medians \pm credible intervals along with individual ratio to baseline or change from baseline values based on the endpoints will be presented.

Joint model

In addition to the Bayesian MMRM analysis, the ratio to baseline or change from baseline based on the endpoints for the following four key biomarkers will be modelled using a multivariate Bayesian analysis including only the placebo and GSK2330811 300mg arms:

- Alpha SMA (Excluding Insufficient samples)
- CCL2 gene assessed from the skin sample through RNA sequencing
- PIIINP assessed from the serum sample
- 2GSSc

Non-informative priors will be used for all parameters. The variance-covariance matrix for the within subject error across the endpoints will use an inverse-Wishart prior distribution consisting of the identity matrix and 4 degrees of freedom.

The model will be adjusted for endpoint (allows each endpoint to have their own intercept), treatment by endpoint interaction term, MMF use at day 1 by endpoint interaction, and baseline by endpoint interaction term. If the model does not converge, the covariate for MMF use will be removed from the model.

Missing baseline covariates will be modelled as part of the MCMC sampling prior to fitting the joint model, using non-informative priors. For example, if b_i is the baseline of the ith endpoint then $b_i \sim N(\theta_i, \delta_i)$ where $\theta_i \sim N(0, sd=100)$ and $\delta_i \sim iGamma(shape=0.1, scale=0.1)$.

For modelling purposes, the log transformed endpoints will be back transformed for the presentation of results. Fold change will also be presented for only log transformed endpoints, posterior medians as, ratio < 1 then fold change is -1/ratio otherwise fold change is ratio.

Heat Plots

Heat plots will be produced for the gene expression endpoints contributing to a gene signature using fold change from baseline. Fold change in Placebo, GSK2330811 100mg and GSK2330811 300 mg at day 85 will be presented in three columns using the 3-fold change cut off. Plot colour scales from blue to white to red scale, values above 3 or below -3 fold change will all be presented using the same colour.

Heat plots are produced for each individual gene from Disease Signature, Lung Fibrosis signature and Cell module signatures as mentioned in Section 13.1.1.3. Within each signature, genes are ordered based on 'Ward' clustering algorithm.

For further reference, heat plot with dendogram for full gene panel contributing to the different signatures will be produced and saved in Refdata folder.

201247

Additional Post SAC transcriptomics analysis will be conducted and the details will be documented in a separate analysis plan.

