13.1.2. Summary Measure

Interim 2:

The baseline values will be summarised without treatment groups using the safety population presenting summary statistics assuming a skewed distribution for the systemic markers. A scatter plot of the raw baseline values will be presented alongside the geometric mean \pm standard error.

The Spearman's and Pearson's correlations of the baseline values transformed using log base 10, will be calculated and presented for each combination of endpoints. The correlations will also be presented as scatter plots for each pair of endpoints. Where both the correlations are >-0.3 and <0.3 the correlation will be suppressed from the outputs.

Final analysis

Standard summaries at each planned timepoint will be used for biomarker endpoints assuming a skewed distribution. The ratio of the post-baseline to baseline values and fold change (geometric ratio <1 then fold change is -1/geometric ratio otherwise fold change is geometric ratio) will also be summarised.

Systemic biomarkers will be summarised and presented using a log 10 scale while the histology and gene sets will be summarised and presented using a log 2 scale. 2GSSc skin biomarker and GSVA Scores will be summarised and presented on linear scale.

Line plots of the unadjusted geometric means \pm standard error for log transformed data and unadjusted means \pm standard error for linear data will be presented by treatment group at each visit. Individual participant plots of the raw values will be presented by treatment group and individual plot lines are differentiated by MMF use at Day 1 (solid

201247

line denote subjects on mycophenolate at day 1 and dashed line denote subjects not in mycophenolate at day 1). Information on positive autoantibodies is added to the subject ids in the legend as per Section 6.1.

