16.6.6. Biomarkers

Derived Parameters for Fibrosis and Histology
ELF
The ELF test will be provided by the vendors using on the ADVIA Centaur system. For reference, here is the formula as specified in the laboratory manual (Rev. C, 2015-01).
The ELF score can be calculated manually or by the ADVIA Centaur systems. For detailed information about how the system calculates results, refer to the system operating instructions.
Note The auto-calculation feature is only available for the ADVIA Centaur XPT system, for the ADVIA Centaur XP system software version 7.0 or higher, and for the ADVIA Centaur CP system software version 6.0 or higher. For the ADVIA Centaur system, and earlier versions of the ADVIA Centaur XP and ADVIA Centaur CP systems, calculate the ELF score manually.
To calculate the ELF score manually for the ADVIA Centaur and ADVIA Centaur XP systems, first obtain results for the ADVIA Centaur HA, PIIINP, and TIMP-1 assays, and then use the following equation to calculate the ELF score:
ELF score = $2.278 + 0.851 \ln(C_{HA}) + 0.751 \ln(C_{PIIINP}) + 0.394 \ln(C_{TIMP-1})$
Concentrations (C) of each of the constituents are in ng/mL.
To calculate the ELF score manually for the ADVIA Centaur CP system, first obtain results for the HA, PIIINP, and TIMP-1 assays on the ADVIA Centaur CP system, and then use the following equation to calculate the ELF score:
ELF score = $2.494 + 0.846 \ln(C_{HA}) + 0.735 \ln(C_{PIIINP}) + 0.391 \ln(C_{TIMP-1})$
Concentrations (C) of each of the constituents are in ng/mL.
Note The ELF score is a unitless numerical value.
Alaba SMA
αSMA= αSMA Area (μm²)/(Dermis Area).
2GSSc Skin Biomarker
2GSSc = -27.6844 + (4.46*(Baseline THBS1)) + (5.31*∆MS4A4A) + (4.96*∆THBS1)
Where, Δ MS4A4A and Δ THBS1 are change from baselines and Baseline THBS1 is baseline value of THBS1 on log 2 scale
General
If biomarker values are below the lower limit of quanitification, data will be imputed as half the lower limit of quantification (LLQ).

If biomarkers are above the upper limit of quantification, data will be imputed as for lab data, where the number of decimal places in the observed values will be used to determine how much to add in order to impute the corresponding numeric value:

- Example 1: 2 decimal places: '> x' becomes x + 0.01
- Example 2: 1 decimal places: '> x' becomes x + 0.1
- Example 3: 0 decimal places: '> x' becomes x + 1

201247

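### ELF is already a sum of natural logs, but the SAP logs it again and reports a ratio and fold change; the size of that ratio has no stable meaning and its interval mostly reflects the prior

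*SAP*

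**What the plan says.** SAP 16.6.6 gives the ELF formula for the ADVIA Centaur and XP analysers as 2.278 + 0.851 ln(HA) + 0.751 ln(PIIINP) + 0.394 ln(TIMP-1), with concentrations in ng/mL. The CP analyser has a different constant (2.494) and slightly different slopes. The section adds that "The ELF score is a unitless numerical value".

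SAP 13.1.5 (Longitudinal model) states: "The ratio to baseline for the following systemic biomarkers will be analysed using a Bayesian MMRM analysis using the log transformed data". ELF is on that list beside concentrations such as PIIINP and IL-6, with no separate rule. Treatment effects "are back transformed to give the ratio to baseline and the ratio of the change relative to placebo respectively", and the outputs include "the probability the ratios are <1 and fold changes". The covariance prior is an "inverse-Wishart prior distribution, consisting of the identity matrix and the degrees of freedom will be the number of visits" in the model, and the priors are described as non-informative.

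SAP 13.1.2 sets the display scale: "Systemic biomarkers will be summarised and presented using a log 10 scale while the histology and gene sets" go on log 2. The exceptions are named: "2GSSc skin biomarker and GSVA Scores will be summarised and presented on linear scale". ELF is not among them. The log base used inside the MMRM is not stated.

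**The concern.** Logging a concentration turns proportional changes into differences, which back-transform to ratios with a plain meaning. ELF has already had that step. A difference in ELF is a weighted sum of log ratios of its three components. A ratio of two ELF scores is not a fold change in anything measured, because its size depends on the baseline score, the additive constant and the concentration unit.

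Two things are at stake. First, ELF's fold change would appear in the same tables as PIIINP's and invite a comparison that is not valid: a large movement in the components would look trivial. Second, the covariance prior has unit scale. Values of log ELF vary by a few hundredths, so the prior rather than the data would set the width of the credible interval, and the probability that the ratio is below 1 would be pulled towards 0.5.

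**Working it through.** **Inputs from the documents.** ELF slopes: SAP 16.6.6. Post-baseline blood-biomarker visits: Days 29, 57, 85 and 197 (schedule of activities), so the prior is IW(I, 4). Planning size: 15 active and 5 placebo (Protocol 10.1). SD of log(PIIINP): 0.521 (Protocol 10.1), taken here as natural log.

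**Assumed.** ELF level 7 to 11 and residual SD 0.2 to 1.04 units; the documents give neither. Anchors from 0.521:
- PIIINP alone: 0.751 × 0.521 = 0.39.
- All three components with that SD, independent: 0.521 × √(0.851² + 0.751² + 0.394²) = 0.63.
- All three with that SD, perfectly correlated: 0.521 × 1.996 = 1.04.
- Lower values allow for baseline adjustment.

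**The plan's nearest figure.** Protocol 10.1 states a 95% half-width of 0.565 for log(PIIINP). t(0.975, 18) × 0.521 × √(1/15 + 1/5) = 0.565, so it reproduces.

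**Interpretation (needs no variance assumption).** The slopes sum to 0.851 + 0.751 + 0.394 = 1.996. Doubling all three markers adds 1.996 × ln 2 = 1.38; a 30% fall in all three adds 1.996 × ln 0.7 = −0.71.

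| Baseline ELF | Ratio if all three double | Ratio if all three fall 30% |
|---|---|---|
| 8 | 1.17 | 0.911 (fold change −1.10) |
| 9 | 1.15 | 0.921 (fold change −1.09) |
| 11 | 1.13 | 0.935 (fold change −1.07) |

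The true component ratios are 2.0 and 0.70 in every row.

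**Prior, fitted variance.** With 20 participants and about four coefficients per visit there are 16 residual df. Under IW(I, 4) on four visits, the posterior mean variance at one visit is (1 + 16s²)/(4 + 16 − 4 − 1) = (1 + 16s²)/15, where s is the residual SD on the analysis scale. At level 9, s on ln is about SD/9, and on log10 about SD/(9 × 2.303).

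| SD of ELF change | Native scale | ln | log10 |
|---|---|---|---|
| 0.3 | 1.3 times | 7.8 times | 17.9 times |
| 0.7 | 1.1 times | 3.5 times | 7.7 times |

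Entries are the fitted SD divided by the true SD.

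**Prior, interval for the treatment difference.** With near-common regressors the posterior at a visit is Student t on 17 df with scale² = (1 + S)/17 × (1/15 + 1/5), where S = 16s². The 1 comes from the prior, so its share of the sum of squares is 1/(1 + S). The reference without the prior is t(16) × s × √(1/15 + 1/5).

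Example, level 9 and SD 0.4, centred on a ratio of 1:
- ln: s = 0.0444, S = 0.032, prior share 97%, interval 0.76 to 1.31.
- log10: s = 0.0193, S = 0.006, prior share 99%, interval 0.54 to 1.84.
- Without the prior: 0.95 to 1.05.

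Over the full assumed range the prior supplies 74 to 99% of the sum of squares on ln and 94 to 100% on log10. Intervals are 1.9 to 13 times and 3.9 to 31 times as wide as without it. At 27 versus 9 (the maximum cohort 2 size of 36, split 3:1) and level 9, inflation is still 1.8 to 7.9 on ln and 3.6 to 18 on log10.

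**Simulation check.** A Gibbs sampler for the full SAP model, compared with a near-flat covariance prior at level 9 and SD 0.3 / 0.5 / 0.8, gave inflation of 9.1 / 4.6 / 2.9 on ln, 17.6 / 11.7 / 6.5 on log10 and 1.29 / 1.09 / 1.06 on the native scale.

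**Comparison.** PIIINP, for which one log is appropriate, has interval inflation of 1.07 on ln and 1.44 on log10.

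**The case against.** ELF is positive in practice, so its log is a monotone transform: the direction of effect survives, and the probability of a ratio below 1 asks the same directional question as the probability of a difference below 0. This stands, and it is why the defect lies in magnitude and precision rather than direction. That probability is still attenuated by the inflated variance.

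The SAP's linear treatment of 2GSSc and GSVA may reflect necessity rather than principle, since GSVA scores lie between −1 and 1 and 2GSSc can be negative. This is fair. The case against the second log rests on ELF's own formula, not on the analogy. Nor do the documents suggest that analysers were mixed within the study, so the differing constants show only that the zero point is a convention.

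HA, PIIINP and TIMP-1 have their own summaries, and PIIINP its own model, so a doubling would be visible elsewhere. Baseline terms in the model absorb part of the baseline dependence. Both points limit the harm but do not make the ELF output right.

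The covariance prior applies to every marker on the list and is a separate weakness, which moving ELF does not cure. That is correct, but the second log is what turns a modest effect into a dominant one for ELF.

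Finally, ELF is exploratory: it is not among the four joint-model biomarkers, is not in the clinical correlation table and drives no stated decision rule. This caps the importance.

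**Conclusion.** The concern holds. As written, the plan logs a score already on a log scale and reports a ratio and fold change whose size depends on baseline and on an additive constant. That part follows from the SAP's own formula and needs no assumption.

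The size of the prior's effect rests on an assumed ELF level and SD, and on whether the model uses ln or log10. The conclusion is not sensitive to them. At 15 versus 5, the prior's share falls below one half only when s exceeds 0.25, which at level 9 means about 2.25 ELF units on ln (0.25 × 9) or about 5 on log10 (0.25 × 9 × 2.303). Both exceed the highest anchor of 1.04.

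The primary safety objective is not affected. The SAP should be corrected because the ELF result would otherwise mislead on both size and precision.

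**What to change.** In SAP 13.1.5, take ELF off the log-ratio list and fit the same MMRM to its change from baseline on the native scale. Report the posterior median difference, the 95% credible interval and the probability that the difference is below 0, and drop the ratio and fold change. In SAP 13.1.2, add ELF to the scores summarised on the linear scale.

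Both pieces already exist: SAP 14.1.5 fits this longitudinal model to untransformed change for mRSS, HAQ-DI and laboratory FVC, and the linear output format is in the ANCOVA part of 13.1.5. The cost is wording, a model option and separate handling of ELF in Tables 8.2 to 8.4 and Figures 8.2 to 8.4.

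On the native scale at 15 versus 5, the half-width is 0.41, 0.50 or 0.69 ELF units at SD 0.3, 0.4 or 0.6, against 0.33, 0.44 or 0.66 without the prior. Some inflation remains at small SDs (1.55 times at SD 0.2). A covariance prior scaled to the data, or a sensitivity analysis on it, would deal with the rest and would help the other logged markers. The log base used in the MMRM should also be stated.

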14.1. Exploratory Efficacy Analyses

14.1.1. Endpoint / Variables

The analyses of clinical disease assessments (preliminary assessment of efficacy in Systemic Sclerosis) will be based on the Per Protocol population, unless otherwise specified. They will consist of the following endpoints:

- mRSS
- HAQ-DI
- SHAQ VAS scales
- PhGA
- PtGA
- CRISS (derived non-parametric summaries)
- Laboratory FVC (L) (Note: impact of treatment on the rate of change will be inferred from the Figures)
- % predicted laboratory FVC
- Weekly Home FVC (L) (Note: impact of treatment on the rate of change will be inferred from the Figures)

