14.1.5. Statistical Analyses / Methods

Details of the planned displays are provided in Appendix 12 and will be based on GSK Data Standards and statistical principles.

201247

The endpoints / variables defined in Section 14.1.1 will be summarised using descriptive statistics, graphically presented (where appropriate) and listed.

Longitudinal model

Longitudinal Bayesian model as specified in Section 13.1.5 will be fitted for the change from baseline in the following endpoints:

- mRSS
- HAQ-DI
- Laboratory FVC (L)

The difference in the differences from baseline will be calculated across the treatment groups (GSK2330811 300mg – placebo).

Posterior means and equal tailed 95% credible intervals will be presented. In addition, except for Laboratory FVC, the probability the differences are <0 will be calculated and for Laboratory FVC, differences are >0 will be calculated. The line plots of the adjusted posterior mean change from baseline \pm credible intervals at each visit will be presented.

Non-Parametric Analysis

The CRISS endpoint is not expected to be normally distributed and so will be analysed using Bayesian non-parametric techniques including only placebo and GSK2330811 300mg arms.

Observed data from two groups are assumed to come from an underlying latent normal distributions with unit variance. Observations from these two latent normal distributions are generated from the truncated normal distributions in such a way to maintain the ordinality of the data. The parameter of interest is difference in the two latent means, δ . Prior distribution of δ , will be Cauchy distribution with shape parameter 0.5 and scale parameter $1/\sqrt{2}$. To obtain the posterior distribution for δ , analysis will follow the algorithm advocated by van Doorn, 2020.

Probability difference > 0 will be presented.

Boxplots of the predicted probability of improvement from baseline in the CRISS endpoints at day 85 and day 197 will be presented by treatment group.

Correlation Analysis

In addition, correlation analysis will be performed at Day 85 for set of endpoints listed below. The correlation will be presented as scatter plots of endpoints for each of the treatment groups, including the Pearson correlation coefficient. For ratios, correlations will use the log transformed data while the plot will present the untransformed data with the appropriate axis presented on the log scale.

- For each combination of change or ratio of key biomarkers

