16.12.17. Biomarker Figures

Biomarker: Figures						
No.	Population	IDSL / Example Shell	Title	Programming Notes	Deliverable [Priority]	
Systemic bio	markers					
8.1	Safety	BIO_F1	Panel Plot of Baseline Levels of Systemic Biomarkers	Baseline values only, jittered scatter plot with superimposed geometric mean and standard error bars. Page 1 (2x4 plot): C3M, C6M, C1M, COMP, PINP, Pro-C3, Pro-C6 Page 2 (2x2 plot): HA, TIMP-1, PIIINP, ELF Page 3 (1x3 plot): Pro-C3/C3M, Pro- C6/C6M, PINP/C1M Page 4 (2x2 plot): CRP, IL-6, CCL2, CCL-18 (PARC1) Page 5 (2x2 plot): vWF, VEGF, sVCAM-1, NT-ProBNP Note: plot using order above. Exclude C1M results using mouse hybridoma cell line as small sample size may be unblinding. Add footnote 'Note: C1M assay changed during the study. C1M results not presented for samples analysed using the old C1M (denoted C1M*) kit due to small sample size and potential unblinding. New C1M kit denoted as C1M+	IA2	

Biomarker: Figures							
No.	Population	IDSL / Example Shell	Title	Programming Notes	Deliverable [Priority]		
8.2	Per Protocol	BIO_F2	Line Plot of Systemic Biomarkers	Line plot of three treatment arms. page by biomarker, ordered by endpoint type (Inflammation, Fibrosis, Vascular) Y-axis presented to log base 10 scale. Note: No. of subjects with results below the lower limit of quantification, assigned to half of the lower limit of quantification. Note: C1M assay changed during the study. Results using old kit denoted as C1M* and new kit denoted as C1M+.	SAC		
8.3	Per Protocol	BIO_F2	Line Plot of Analysis of Ratio to Baseline of Systemic Biomarkers	For endpoints as specified in Section 13.1.5.	SAC		
8.4	Per Protocol	BIO_F4	Individual Subject Profiles of Systemic Biomarkers	Panel by treatment, page by biomarker, ordered by endpoint type (Inflammation, Fibrosis, Vascular) y-axis presented to log base 10 scale Note: No. of subjects with results below the lower limit of quantification, assigned to half of the lower limit of quantification. Note: C1M assay changed during the study. Results using old kit denoted as C1M* and new kit denoted as C1M+.	SAC		
Histology bio	omarkers		•	·			
8.5	Per Protocol	BIO_F2	Line Plot of Alpha SMA Results	Include both sufficient and insufficient samples. Y-axis presented to log base 2 scale	SAC		

Biomarker: Figures								
No.	Population	IDSL / Example Shell	Title	Programming Notes	Deliverable [Priority]			

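### The inverse-Wishart(identity) prior in SAP 13.1.5 is called non-informative but depends on the outcome's unit, and it widens credible intervals where the residual SD is well below 1 (most likely laboratory FVC in litres)

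*SAP*

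**What the plan says.** For the longitudinal model of systemic biomarkers, SAP 13.1.5 states: "Non-informative priors will be used in these analyses, specifically the prior for the regression coefficient will be normally distributed" with mean 0 and a very large variance. The within-subject covariance matrix across visits "will use an inverse-Wishart prior distribution, consisting of the identity matrix and the degrees of freedom will be the number of visits" in the model. The joint model of four key biomarkers is also said to have non-informative priors throughout, and its covariance matrix "will use an inverse-Wishart prior distribution consisting of the identity matrix and 4 degrees of freedom".

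SAP 14.1.5 reuses the longitudinal model for mRSS, HAQ-DI and laboratory FVC: "Longitudinal Bayesian model as specified in Section 13.1.5 will be fitted for the change from baseline in the following endpoints". The FVC unit is fixed in 14.1.1: "Laboratory FVC (L) (Note: impact of treatment on the rate of change".

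The log base of the model is not named. The systemic markers are analysed "using a Bayesian MMRM analysis using the log transformed data including only the placebo and GSK2330811 300mg arms". Log10 appears only for summaries and displays: 13.1.2 has systemic markers "using a log 10 scale while the histology and gene sets will be summarised and presented using a log 2 scale", and the note to Figure 8.2 in 16.12.17 says "Y-axis presented to log base 10 scale".

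The skin ANCOVA in the same section uses a different variance prior, inverse-gamma(0.001, 0.001). Section 13.1.5.1 lists convergence diagnostics and no check on the influence of the prior.

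**The concern.** An identity scale matrix is a statement about size in the outcome's own unit. It says that each variance is of the order of 1, whether the outcome is in litres, log10 ng/mL or skin-score points. If the true residual variance is far below 1, the prior supplies a large part of the variance estimate in a trial with 20 to 36 cohort 2 participants, as few as 5 of them on placebo.

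Credible intervals and posterior probabilities are the planned inference for these endpoints. For an affected endpoint they would reflect the choice of unit as well as the data, and a real pharmacodynamic or FVC signal would be reported as less certain than the data show. A converged chain would not reveal this.

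**Working it through.** **Inputs.** Prior: SAP 13.1.5. Post-baseline visits: 4 for blood biomarkers and 2 for laboratory FVC (schedule of activities). Regression terms per visit: 4 (intercept, treatment, baseline, mycophenolate use). N = 20 (15 v 5) or 36 (27 v 9), and an SD of 0.521 for log(PIIINP) with no base stated: protocol 10.1. FVC residual SD: not in the documents; 0.1 to 0.5 L is assumed.

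**The protocol's own figure.** t(0.975, 18) × 0.521 × √(1/15 + 1/5) = 2.101 × 0.521 × 0.516 = 0.565, as stated. So 0.521 serves there as the SD of the treatment comparison.

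**What the prior does.** For an inverse-Wishart with identity scale and df equal to its dimension, each diagonal element is inverse-gamma(1/2, 1/2), whatever the dimension. The prior median SD is 1.48, and the prior probability of an SD below 0.2 is about 6 in 10 million. With d = N − 4 and S = d·s²:

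- ordinary t half-width: t(0.975, d) × s × g
- half-width under the SAP prior: t(0.975, d+1) × √[(S+1)/(d+1)] × g

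Here g = √(1/n₁ + 1/n₀), which cancels in the ratio.

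**Thresholds against the t interval.** The ratio exceeds 1.10 when s is below 0.46 (N=20) or 0.35 (N=36), and 1.25 when s is below 0.30 or 0.23.

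**FVC in litres (SD assumed).** At 0.2 L and N=20, S = 16 × 0.04 = 0.64. The t half-width is 2.120 × 0.2 × 0.516 = 0.219 L. Under the SAP prior it is 2.110 × √(1.64/17) × 0.516 = 0.338 L, a ratio of 1.55.

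| Residual SD (L) | N=20 | N=36 |
|---|---|---|
| 0.1 | 2.60 | 2.00 |
| 0.2 | 1.55 | 1.31 |
| 0.3 | 1.26 | 1.14 |
| 0.4 | 1.14 | 1.08 |
| 0.5 | 1.08 | 1.04 |

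At 0.2 L, a posterior probability of 0.975 becomes 0.905 (N=20) or 0.935 (N=36). The same data in mL give 0.97 or 0.98, so the unit alone changes the answer. Against the multivariate Jeffreys prior, 0.2 L gives 1.49 (N=20) and 1.29 (N=36).

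**PIIINP.** What matters is the residual SD on the model scale.

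- Modelled on log10, with 0.521 a natural-log SD: s = 0.521/2.303 = 0.226 and S = 0.82. The ratio is 1.44 v t and 1.27 v Jeffreys at N=20; 1.25 and 1.18 at N=36.
- With 0.521 as the residual SD on the model scale: 1.07 v t and 0.95 v Jeffreys at N=20; 1.04 and 0.985 at N=36.
- If 0.521 is a log10 SD but baseline adjustment lowers it (assumed correlation 0.5 or 0.8): 1.10 or 1.24 v t at N=20. If it is a natural-log SD modelled on log10: 1.57 or 2.02.

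**Simulation check.** The formula treats each visit separately with complete data. Gibbs fits of the model as written, including the shared mycophenolate term, agree. At N=20, FVC at 0.2 L gave 1.65 (SE 0.05) against a near-zero-scale reference and 1.49 against Jeffreys; PIIINP at 0.226 gave 1.38 (SE 0.04) and 1.31. Posterior medians shifted by 0.6 to 2.2% of the half-width.

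**Not affected.** mRSS at an assumed SD of 3 to 5 gives 0.97 (N=20). The skin ANCOVA has its near-flat prior, CRISS has its own model, and the primary safety endpoints have no such model. HAQ-DI and the other systemic markers are affected only if their residual SD falls below the thresholds; the documents give no SD for them.

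**The case against.** The strongest reply has four parts.

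- **No affected endpoint can be proved from the documents.** This stands. There is no FVC SD, and at 0.5 L the effect is 8% or less. The mechanism is certain; its size is conditional.
- **Too wide depends on the reference.** This stands for PIIINP, where the sign reverses against Jeffreys at an SD of 0.521. It does not rescue FVC at a small SD, which widens under either reference.
- **A comparison is already built in.** This stands in part. Alpha SMA, skin CCL2 and 2GSSc are fitted both in the joint model and by ANCOVA with inverse-gamma(0.001, 0.001) at Day 85, so those pairs can be compared. The longitudinal endpoints and joint-model PIIINP have no such pair. Unadjusted summaries and plots allow only an informal look.
- **The choice is a usual default.** Degrees of freedom equal to the dimension is the smallest integer that keeps the prior proper. That is so, but the difficulty is the unscaled identity matrix.

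Two stronger readings are tempting. A reader might infer that PIIINP intervals will be 44% too wide. The documents do not support that: the base of 0.521 and the base of the model are both unstated, and log10 is given only for summaries and displays. A reader might also infer that the trial's conclusions are compromised. They are not: protocol 3.1 says no formal hypothesis is tested, SAP 2.4.1 and 2.4.2 plan no statistical analysis of primary or secondary endpoints, and where intervals widen the error is conservative.

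**Conclusion.** The point holds as a low-severity error in an exploratory analysis. The prior is not non-informative: it adds 1 df and 1.0 to each residual sum of squares in the outcome's unit, and nothing in 13.1.5.1 would show its effect.

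Laboratory FVC in litres is the endpoint most likely to be affected, but its size rests wholly on assumed SDs. For PIIINP, a material effect needs log10 modelling together with either a natural-log reading of 0.521 or a substantial fall in residual SD from baseline adjustment. All multiples assume four terms per visit, complete data and the cohort 2 numbers. One cohort 1 placebo participant added to the placebo arm changes little: 1.44 becomes 1.42 for PIIINP on log10 with a natural-log 0.521.

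**What to change.** 1. In 13.1.5, state the log base used in the longitudinal and joint models. If the display bases carried over, the joint model would apply the same 1.0 to PIIINP on log10, alpha SMA and CCL2 on log2, and 2GSSc on a linear scale.
2. Scale the prior to each outcome. One way is to divide by the pooled residual SD, fit with the existing prior and back-transform; the ratio to the t interval is then 0.995 (N=20) or 0.999 (N=36). The other is half-t priors on the SDs with a stated wide scale and a weakly informative correlation prior; a scale of 10 gave 1.01 to 1.05 in simulation for SDs of 0.2 to 0.52. If neither is adopted, drop the non-informative label.
3. Add to 13.1.5.1 one prior-sensitivity fit for the longitudinal endpoints, chiefly FVC, and for PIIINP in the joint model, naming the reference prior.

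Cost: SAP wording, a few lines of code and one extra run per endpoint, with no new data. Standardising takes its scaling SD from the trial data; the half-t option needs slightly more code and a chosen scale.
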